Unfortunately, nearly all glioblastomas recur or progress within 7 months of initial diagnosis ([Alifieris 2015](#)). Second-line chemotherapy regimens include temozolomide; nitrosureas; combination procarbazine, CCNU (lomustine), and vincristine (PCV); cyclophosphamide; and platinum-based regimens. The antiangiogenic agent, bevacizumab (Avastin), received accelerated approval in the United States in 2009 for recurrent glioblastoma based on modest improvements in overall response rate (ORR) and median duration of response (DOR) in an open-label, randomized, noncomparative, multicenter study of bevacizumab with or without irinotecan and in a single-arm, single

institutional trial; ORRs were 25.9% (in the bevacizumab-containing arm) and 19.6%, respectively, and median DORs were 4.2 months and 3.9 months, respectively (AVASTIN prescribing information). However, use of bevacizumab (Avastin) is associated with potential serious adverse events (SAEs), including hypertension, impaired wound healing, colonic perforation, and thromboembolism ([NCCN Guidelines 2015](#)). Hence, a large unmet need exists in the treatment of newly diagnosed and recurrent GBM.

1.2 BRUTON TYROSINE KINASE INHIBITION IN CANCER

Acalabrutinib is a covalent inhibitor of Bruton tyrosine kinase (BTK), a non-receptor enzyme in the Tec kinase family, which also includes bone marrow X-linked (BMX) nonreceptor tyrosine kinase.

BTK-dependent activation of mast cells, myeloid cells, and other immunocytes in peritumoral inflammatory stroma has been shown to sustain the complex microenvironment needed for lymphoid and solid tumor maintenance ([Soucek 2011](#), [de Rooij 2012](#), [Ponader 2012](#)). Inhibition of BTK may impair the capacity of tumor-associated macrophages to promote tumor invasion and metastasis ([Mouchemore 2013](#)). Several lines of evidence demonstrate that BTK inhibition interferes with cross-talk between malignant cells and their microenvironment ([Ponader 2012](#), [Herman 2013](#)). BTK is also a signaling hub in myeloid-derived suppressor cells (MDSCs), which may play an important part in the suppression of antitumor immune responses, creating an immunosuppressive environment necessary for the growth of malignant cells ([Schmidt 2004](#), [Wesolowski 2013](#), [Condamine 2014](#)).

In addition, BTK and BMX have been shown to be expressed in gliomas. Across a panel of various cancer types, gliomas show the highest levels of BTK expression, second only to lymphomas ([Uhlén 2015](#)). BMX is preferentially expressed in glioblastoma stem cells (GSCs) and activates STAT3 signaling, playing an essential role in maintaining the stem cell phenotype and tumorigenic potential ([Guryanova 2011](#)). Taken together, these findings suggest that inhibition of BTK and BMX may offer an attractive strategy for targeting GBM.

1.3 ACALABRUTINIB

Acalabrutinib is an imidazopyrazine analogue with a molecular weight of 465.5 g/mol. The compound has 1 stereogenic center and acalabrutinib is the S-enantiomer. Acalabrutinib is orally administered in humans and is suitable for formulating in capsules.

For clinical testing, acalabrutinib has been manufactured and formulated according to current Good Manufacturing Practices (cGMP).

Calquence® has been approved in the United States and other markets for the treatment of adult patients with mantle cell lymphoma (MCL) who have received at least one prior therapy, chronic lymphocytic leukemia (CLL), and small lymphocytic lymphoma (SLL).

1.3.1 Mechanism of Action

CCI [REDACTED]
[REDACTED] Acalabrutinib was specifically designed to be a more potent and selective inhibitor of BTK to avoid off-target side effects seen with other BTK inhibitors. CCI [REDACTED]
[REDACTED]

1.3.2 Safety Pharmacology

In vitro and in vivo safety pharmacology studies with acalabrutinib have demonstrated a favorable nonclinical safety profile; for detailed information on the safety pharmacology of acalabrutinib, refer to the Investigator Brochure.

[figure not shown]
1.3.3 Drug-Drug Interaction Potential

For more detailed information on drug-drug interaction potential for acalabrutinib, refer to the Investigator Brochure. Please refer to [Section 3.9.6](#) for guidance on drugs that may cause drug-drug interactions.

1.3.4 Acalabrutinib and the Blood-Brain Barrier

Acalabrutinib is a P-glycoprotein substrate, which may contribute to the relatively low brain exposure observed in nonclinical studies in rats. In a biodistribution study in rats using radiolabeled acalabrutinib, low relative concentrations (3 to 4% of plasma concentrations) were observed in the brain. Brain pharmacokinetic (PK) experiments were performed to evaluate the potential for acalabrutinib to cross the blood-brain barrier. Four Sprague-Dawley rats per group were treated with acalabrutinib by oral gavage at 5 or 30 mg/kg/day and tissues were collected at 30 minutes after dosing on Days 1, 3, and 5. Two vehicle-treated rats were also sacrificed on each sampling day for comparison. Cerebral spinal fluid (CSF) was collected, and then the brains were flushed with heparinized saline prior to collection and snap-frozen for analysis of acalabrutinib levels. Bioanalytical methods specific to CSF and brain tissue were used to measure acalabrutinib levels.

Figure 1-1: Acalabrutinib Levels in Rat Brain Tissue and CSF

ACP-196 = acalabrutinib; CSF = cerebral spinal fluid.

The ratio of acalabrutinib in the flushed brains, compared with matched plasma concentrations, showed that brain extracts had approximately 3 to 4% of the observed plasma concentrations, consistent with the results from the radiolabeled biodistribution study. The ratios observed in clean cerebral spinal fluid samples from rats treated with 5 and 30 mg/kg/day were between 1 to 2% of the plasma levels. BTK target occupancy results showed 71 to 88% in the brain samples (see [Table 1-1](#)).

Table 1-1: BTK Target Occupancy in Rat Brain Tissue

Timepoint	Dose Level	
	5 mg/kg/day	30 mg/kg/day
Day 1	23%	54%
Day 3	62%	82%
Day 5	71%	88%

1.4 CLINICAL EXPERIENCE – ACALABRUTINIB

Acalabrutinib has been studied in a broad range of clinical studies, including subjects with hematologic malignancies and solid tumors. No new safety concerns were identified for acalabrutinib monotherapy based on safety data available to date. The safety data of acalabrutinib monotherapy are consistent among studies. For more detailed and updated information on the clinical experience for acalabrutinib, please refer to the Acalabrutinib Investigator Brochure.

1.5 BENEFIT/RISK

Acalabrutinib is a potent, orally administered small-molecule inhibitor of BTK. In the Phase 1/2 study of acalabrutinib in subjects with CLL or Richter's syndrome (ACE-CL-001; Section 1.4.2), no dose-limiting toxicities (DLTs) were identified at any evaluated dosages, which included dosages up to 400 mg once per day (QD) or 100 to 200 mg twice per day (BID). The ORR in the evaluable subjects for this study is 95% (Byrd 2016).

Given the high unmet need in patients with glioblastoma, new therapies are needed. Acalabrutinib has been administered to subjects with hematologic malignancies, healthy volunteers, and subjects with mild or moderate hepatic impairment. *See the Acalabrutinib Investigator Brochure for further details.*

Acalabrutinib 200 mg BID and 400 mg QD have been well tolerated by subjects with CLL (ACE-CL-001). *See the Acalabrutinib Investigator Brochure for details.* The preclinical hypothesis of altering the tumor microenvironment as well as the potential direct on target inhibition of BTK in gliomas warrants further study into the activity of acalabrutinib in GBM.

2.0 STUDY OBJECTIVES

2.1 PRIMARY OBJECTIVES:

- To characterize the safety profile of acalabrutinib monotherapy in subjects with recurrent GBM
- To evaluate the efficacy of acalabrutinib monotherapy in subjects with recurrent GBM based on ORR per the Response Assessment in Neuro-Oncology (RANO) criteria

2.2 SECONDARY OBJECTIVES:

- To evaluate the efficacy of acalabrutinib monotherapy based on DOR per RANO criteria
- To evaluate the efficacy of acalabrutinib monotherapy based on progression-free survival (PFS) per RANO criteria
- To evaluate the efficacy of acalabrutinib monotherapy based on PFS-6 rate per RANO criteria
- To evaluate the efficacy of acalabrutinib monotherapy based on OS

2.3 EXPLORATORY OBJECTIVES:

CCI

CCI

3.0 STUDY DESIGN

This Phase 1b/2, multicenter, open-label study is designed to evaluate the efficacy and safety of acalabrutinib in subjects with recurrent GBM who have progressed after 1 or 2 prior systemic treatment regimens. Subjects meeting the eligibility criteria for the study will be assigned 1:1 to one of the following cohorts:

Cohort 1: acalabrutinib 200 mg administered orally (PO) BID

Cohort 2: acalabrutinib 400 mg PO QD (see note below)

An interim safety and efficacy analysis will occur approximately 8 weeks (2 cycles) after the 12th subject has been enrolled in each cohort in the Phase 1b portion of the study. Enrollment in each cohort will be held after the 12th subject has been enrolled while the interim safety and efficacy results are reviewed by a Scientific Advisory Committee (SAC) in collaboration with the Safety Review Committee. If acceptable safety and efficacy (e.g., 2 or more of the 12 subjects [$\geq 16.7\%$] achieve a complete response ([remission] CR) or PR; additional criteria may be considered by the SAC) are observed in either cohort, the sponsor may choose to expand the study to a total of 72 subjects. The acalabrutinib dosage for the Phase 2 portion of the study will be based on available safety and efficacy data from the Phase 1b cohorts. Note: depending on the Phase 1b results, the SAC and the Safety Review Committee may recommend continued evaluation of both regimens in the Phase 2 portion of the study. The final analysis will occur 24 weeks after the last subject is enrolled to the study (see note below).

For the purpose of analyzing potential drug-drug interactions, each initial 12-subject cohort will be comprised of 8 subjects who do not require enzyme-inducing antiepileptic drugs (EIAEDs) that are strong cytochrome P450 (CYP) inducers (including carbamazepine, oxcarbazepine, phenytoin, fosphenytoin, phenobarbital, and primidone) and 4 subjects who do require such drugs (see note below).

Subjects will be treated until disease progression, unacceptable drug-related toxicity, death, the start of new anticancer therapy for GBM, consent withdrawal, or are lost to follow-up. All subjects will be evaluated for response using the RANO criteria ([Wen 2010; Appendix 2](#)).

Treatment can continue until the end of trial, defined as 52 weeks after the last subject is enrolled to the study, for subjects without disease progression and who are tolerating therapy. Subjects who have **confirmed** progressive disease or who start new anticancer therapy for GBM will discontinue study treatment.

[figure not shown]
Subjects who are *still on treatment at the end of the study* and deriving clinical benefit from acalabrutinib treatment may continue treatment. *At the time of the final data cutoff (DCO) and database closure, subjects who remain in this study may be transitioned to a separate rollover study or remain within this study for continued access to study drug. Once all active subjects are eligible to continue to receive acalabrutinib and after database closure, this study would be considered closed. There will be no further data collection other than reporting of SAEs per [Section 6.2](#). Access within this study will enable continued treatment with visit assessments per standard of care, whereas the separate rollover study will enable treatment continuation with visit assessments and data collection per the rollover study protocol.*

Refer to [Appendix 1](#) for a comprehensive list of study assessments and their timing. The study schema is provided below ([Figure 3-1](#)).

Note: Under Amendment 2 of the protocol, an interim analysis was scheduled after the 12th subject was enrolled in each arm (n=24). However, due to the paucity of EIAED-treated subjects, an interim analysis was held after 16 non-EIAED subjects and 1 subject on EIAED were enrolled in the study. The first interim analysis did not raise any safety concerns and showed some response in the 200 mg-BID group, while no response in 400-mg QD group. Therefore, the SAC recommended discontinuing Cohort 2 (400 mg QD) and enrolling 7 additional non-EIAED subjects planned for Phase 1b of the study into Cohort 1 (200 mg BID). A second interim analysis for safety and efficacy will be performed after enrolling an additional 7 subjects, once 15 total subjects enrolled in the 200-mg BID cohort (8 subjects enrolled prior to first interim analysis, and an additional 7 subjects planned to complete Phase 1b). An ORR rate of 3/15 (20%) will yield a lower bound of a 1-sided 90% exact binomial CI of 7.1%, which is greater than 5% (ORR estimate for the standard of care CCNU). Based on these

criteria, the SAC and the Safety Review Committee will review data after the 2nd interim analysis and will make a recommendation if study should be continued into Phase 2. If continued, up to 28 additional subjects may be enrolled for a total of 43 subjects on the 200-mg BID dose (15 subjects from Phase 1b and 28 subjects from Phase 2) in order to complete Phase 2. The final analysis will occur 24 weeks after the last subject is enrolled in the study. Treatment will continue until the last enrolled subject experiences disease progression.

Figure 3-1. Study Schema

*Note: Per Protocol Amendment #2, the Scientific Advisory Committee (SAC) observed that response and disease-control rate observed in the 200 mg BID cohort were numerically higher than in the 400 mg QD cohort. Therefore, the 400 mg QD cohort is discontinued.

**Note: Per Protocol Amendment #2, enzyme-inducing antiepileptic drugs (EIAEDs) are no longer considered the standard of care for patients with glioblastoma (Ref. NCCN guidelines version 1 2016). As a result, the requirement for subjects (4 subjects in the 200 mg BID cohort and 3 subjects in the 400 mg QD cohort to receive EIAEDs has been eliminated. One subject receiving EIAEDs has already been enrolled into the 400 mg QD cohort) and will continue to receive treatment per protocol.

BID = twice per day; CYP = cytochrome P450; EIAEDs = enzyme-inducing antiepileptic drugs; GBM = glioblastoma multiforme; ORR = overall response rate; QD = once per day.

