3.3.4 Enrollment Procedures

- Enrollment of a subject into the study will be performed according to the following procedure: The study center will notify the sponsor when a clinically eligible subject is identified and is ready to screen, to ensure enrollment availability on the study.
- After the subject has signed and dated the Informed Consent Form (ICF), all screening procedures have been completed, and eligibility has been confirmed, the subject can be officially enrolled into the study.
- To confirm eligibility the study center will fax/email a completed Enrollment Confirmation Form to the sponsor. The enrollment date will be the date that the Sponsor confirms enrollment.
- The sponsor will aim to fax/email a completed Enrollment Confirmation Form to the study center within 24 hours.

Treatment must begin within the screening window ([Section 4.1](#)).

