4.1.5 Confirmation of Eligibility

Subject eligibility for enrollment will be assessed per [Section 3.3](#). All screening procedures, unless otherwise indicated, should be completed within 21 days of the first dose of study drug.

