5.0 STATISTICAL METHODS OF ANALYSIS

5.1 GENERAL CONSIDERATIONS

Descriptive statistics will be used to summarize baseline demographic and disease characteristics, study drug administration, efficacy, and safety outcomes, PK parameters, and PD markers. Descriptive summaries of discrete data will present the sample size and the incidence as a frequency and as a percentage. Descriptive summaries of continuous data will present the sample size, group mean, standard deviation, median, and range. CIs will be included as appropriate. There are 2 timepoints for analyses: (1) the interim analysis will occur approximately 8 weeks (2 cycles) after the 12th subject has been enrolled in each cohort in the Phase 1b portion of the study, and (2) the final analysis will occur 24 weeks after the last subject is enrolled to the study.

Note: Under Amendment 2 of the protocol, the 2nd interim analysis will be performed approximately when 7 additional non-EIAED subjects complete 16 weeks (4 cycles) of treatment.

Statistical Basis for the Sample Size

The sample size for this study included subjects enrolled in Phase 1b and Phase 2 treated with the same dose regimen. An ORR observed in standard of care for second-line therapies (CCNU) ranged around 5 to 10%. While bevacizumab (Avastin) demonstrated an ORR >20%, considerable toxicities were reported. To reject the null hypothesis of ORR ≤5% in favor of an alternative hypothesis that the ORR is ≥20%, 43 subjects will preserve approximately 88% power to detect the difference at a 0.025 significance level by a 1-sided exact test.

Note: Under Amendment 2 of the protocol, the sample size for this study will include subjects enrolled in Phase 1b and Phase 2 and treated with the same dose regimen. Subjects enrolled in Phase 1b but treated with a different dose regimen not chosen for investigation in Phase 2, will not be included in these sample size calculations.

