5.4.4 Analysis of Efficacy Parameters

Response Rate

ORR is defined as the proportion of subjects who achieve a CR or partial response (remission) (see [Section 4.2](#)). ORR will be calculated, and the corresponding 2-sided exact 95% CI will be derived.

Duration of Response

For subjects who achieve objective response, DOR is defined as the time from the first tumor assessment showing response to the time of confirmed disease progression or death due to any cause, whichever occurs first. Subjects who are still alive and free from progression at the time of data cutoff date, are lost to follow-up, have discontinued from the study, or have initiated other non-protocol antitumor therapy (NPT) will be

censored at the last evaluable tumor assessment. A Kaplan-Meier (K-M) curve will be presented for DOR and K-M median will be calculated with 2-sided 95% CI.

Progression-Free Survival

PFS is defined as the time from first dose to documented disease progression, or death from any cause, whichever occurs first. Subjects who are still alive and free from progression at the time of data cutoff date, are lost to follow-up, have discontinued from the study, or have initiated NPT will have their PFS time censored at last evaluable assessment (or, if there is no post-baseline tumor assessment, at the time of first dose). A K-M curve will be presented, and K-M estimates as well as exact 2-sided 95% CIs will be calculated for event time quartiles, and event-free rates at the protocol-specified disease assessment times.

6-month and [CCI] Progression-Free Survival Rates

PFS-6 rate is defined as the K-M estimate of subjects alive and without documented disease progression at 6 months. In this study, 1 month is defined as 30.4375 days. The K-M method will be used to estimate the PFS-6 rate and corresponding 95% CIs.

[CCI]

Overall Survival

Overall survival (OS) is defined as the time from first dose to death from any cause. Subjects who are still alive at the time of data cutoff date, are lost to follow-up, or have discontinued from the study will have their OS time censored at the last date known to be alive on or before the data cutoff date. The analysis of OS will be conducted, where applicable, using the same analysis method described for PFS.

The SAP will describe analyses of all other exploratory endpoints.

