## **8 FINAL ANALYSIS AND CLINICAL STUDY REPORT**

Planned final analysis will be conducted once last subject exits study, or sponsor decides to close the study, whichever occurs earlier.

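### The protocol's 24-week final analysis falls before the 6-month PFS landmark, and one branch of the SAP's different trigger has no minimum follow-up; the effect on PFS-6 is small

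*Protocol*

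**What the plan says.** **Protocol.** Section 3.0 says: "The final analysis will occur 24 weeks after the last subject is enrolled in the study". Section 5.1 and the synopsis repeat the rule. The 24 weeks run from enrolment, and Section 3.3.4 fixes that date: "The enrollment date will be the date that the Sponsor confirms enrollment". PFS runs from a different origin. Section 5.4.4: "PFS is defined as the time from first dose to documented disease progression, or death from any cause, whichever occurs first". The same section adds "PFS-6 rate is defined as the K-M estimate of subjects alive and without documented disease progression at 6 months" and "In this study, 1 month is defined as 30.4375 days". Appendix 1 (footnote w) schedules MRI at Day 1 of Cycles 3, 4, 6 and 8 and every 8 weeks after that, with a visit window of 3 days either side. Subjects alive without progression are censored at their last evaluable assessment.

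**SAP.** Section 8 gives another rule: "Planned final analysis will be conducted once last subject exits study, or sponsor decides to close the study, whichever occurs earlier". Section 1 says the SAP details the analyses outlined in protocol Amendment 2.0, but nothing in it mentions the 24 weeks or explains the change. PFS-6 is still reported (Sections 4.2 and 10.7.3). Sections 3.1 and 3.2 record that Phase 2 was not recommended and that the analysis covers 24 Phase 1b subjects, 15 on 200 mg BID and 9 on 400 mg QD.

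**The concern.** A landmark estimate needs follow-up that reaches the landmark. Under the protocol's rule the subjects enrolled last cannot be followed to 6 months, and those still event-free are censored further back, at their last scan. A death or an unscheduled progression is dated when it occurs or is documented (SAP Appendix 12.3). Late enrollees without an event therefore leave the risk set at about day 140, while late enrollees with an event before the cutoff stay in as events. That asymmetry pulls the estimate down.

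The loss is not made good later. The 52-week end of trial limits treatment and does not trigger an analysis. Neither document commits to an updated PFS-6. After the final data cutoff and database closure, only SAEs are collected (Protocol Section 3.6).

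**Working it through.** **The plan's own figure.** No follow-up figure is given for PFS-6. The only sample-size figure is about 88% power for ORR (5% against 20%, n = 43, one-sided 0.025, exact test). It reproduces: rejecting at 6 or more responses gives alpha 0.0194 and power 0.885. It does not involve follow-up time.

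**Inputs.** Cutoff at 24 weeks from last enrolment (Protocol 3.0, 5.1). Month of 30.4375 days (5.4.4). Cycle of 28 days, since 2 cycles are 8 weeks (5.1). Scan schedule and window from Appendix 1.

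**Timing from first dose, no dosing lag**
- Cutoff: 24 × 7 = 168 days.
- Landmark: 6 × 30.4375 = 182.6 days. Gap: 182.6 − 168 = 14.6 days.
- Cycle 6 Day 1 scan: 5 × 28 = 140 days (week 20).
- Cycle 8 Day 1 scan: 7 × 28 = 196 days (week 28), window 193 to 199. Gap: 196 − 168 = 28 days (25 to 31).
- No scan is scheduled between weeks 20 and 28.

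**Dosing lag.** The lag from enrolment to first dose is not stated. Section 4.1.5 says "All screening procedures, unless otherwise indicated, should be completed within 21 days of the first dose of study drug", and Section 3.3.4 requires treatment to start within the screening window, so I take 0 to 21 days. The landmark gap becomes 14.6 to 35.6 days and the scan gap 28 to 49 days.

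**Who is affected.** Accrual is not given. At an assumed 2 to 4 subjects per month and no lag, those short of the week-28 scan number 2 × 28/30.4375 = 1.8 to 4 × 28/30.4375 = 3.7. Only those still event-free are censored early.

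**Direction (invented numbers).** Suppose 6 subjects are at risk after week 20, 3 of them late enrollees, and one late enrollee dies on day 155. With adequate follow-up the factor is 5/6 = 0.83. With the 168-day cutoff the other two late subjects are already censored at day 140, and the factor is 3/4 = 0.75. A late enrollee's death between days 168 and 182.6 would be lost, which works the other way. The net average effect is downward.

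**Size.** I simulated the 24-week cutoff against full follow-up. Assumptions: exponential PFS with median 2, 4 or 6 months; 30% of events found off schedule and the rest at the next scheduled scan; random accrual at 2 or 4 per month; no lag; 1,500 runs per scenario.

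| Subjects | Mean shift in PFS-6 (points) | Standard error (points) |
|---|---|---|
| 43 | −0.1 to −0.3 | 6 to 8 |
| 24 | −0.2 to −0.6 | 8 to 10 |
| 15 | −0.4 to −1.1 | 9 to 13 |

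On average 0.5 to 2.7 event-free subjects were censored before the landmark. The standard error changed by less than 0.4 points. With a 7-day lag the largest shift was 1.3 points.

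**SAP trigger.** Waiting for the last subject to exit (death, withdrawal of consent, loss to follow-up or sponsor termination; Protocol 3.11) will normally give more than 24 weeks. The closure branch, joined by whichever is earlier, has no floor. The second interim called for about 16 weeks (112 days) of treatment in the last 7 subjects. That is a partial practical floor, short of both 168 and 182.6 days.

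**The case against.** The best defence is that PFS-6 is defined as a Kaplan-Meier estimate, which does not need every subject observed to 6 months. That stands. Late censoring is mostly administrative, and the residual bias is small. Several stronger readings are tempting, and the documents do not support them.

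- **That only the week-28 scan can inform PFS-6.** Scans at weeks 8, 12 and 20, deaths, clinical deterioration and unscheduled MRIs all determine events before day 182.6. A progression first seen at Cycle 8 Day 1 is dated to that visit, after the landmark. That scan matters only because it keeps event-free subjects in the risk set.
- **That late enrollees contribute nothing after week 20.** Their deaths and unscheduled progressions up to the cutoff count.
- **That the problem concerns 43 subjects.** Phase 2 was not opened. The analysis covers 24 subjects, reported by cohort, and 8 of the 15 on 200 mg BID enrolled before the first interim.
- **That the SAP trigger as a whole shortens follow-up.** Only the closure branch lacks a floor.
- **That the open-ended cutoff lets the sponsor steer results.** The study is open-label and the SAP describes the second interim as already reviewed. But the SAP tests no hypothesis, no decision rule uses PFS-6, and Phase 2 was already not recommended. The concern is speculative.

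**Conclusion.** The point holds as a minor one. The protocol's cutoff is 14.6 days short of the 6-month landmark and 28 days (25 to 31) short of the next scheduled scan, or more with a dosing lag. The two documents give different triggers, and one branch of the SAP's sets no minimum follow-up.

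The consequence is a small loss of information and a slight downward bias in PFS-6: half a point or less in most scenarios and about 1 point in the least favourable no-lag case, a 15-subject cohort accruing at 4 per month. These sizes rest on assumed accrual, median PFS and share of off-schedule events, none of which the documents give. The calendar gaps do not depend on those assumptions. PFS-6 is not invalidated, and ORR and its sample size are untouched.

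**What to change.** State one trigger in both documents: data cutoff at 199 days (about 28.4 weeks) after the last enrolled subject's first dose, which is the Cycle 8 Day 1 scan at 196 days plus its 3-day window. Allow an earlier cutoff only if every subject has progressed, died or left the study. If the study closes sooner, report that PFS-6 follow-up is incomplete and how many subjects were censored before 6 months.

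Naming a date, rather than only a floor, also settles when the analysis happens. The rule gives each subject the opportunity for the scan; it does not guarantee that the scan is done.

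The cost is a cutoff 199 − 168 = 31 days later than the protocol's, about 4 to 5 weeks, plus any lag from enrolment to first dose. It takes one sentence in each document and no extra patients.
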